5.0 ANALYSIS ENDPOINTS

Baseline is defined as the assessment prior to dosing on Day 1 for all assessments other than the where Baseline is defined as the Day -14 assessment.

5.1.1 Primary Endpoint

• Change from Baseline on the PANSS NSFS at Day 84.

5.1.2 Secondary Endpoints

- Change from Baseline on the PANSS NSFS at Days 28 and 56.
- Change from Baseline on the BNSS at Day 84.
- Change from Baseline on the BACS composite score at Day 84.
- Change from Baseline on the CGI-SCH-S score at Day 84.
- CGI-SCH-I score at Day 84.
- Change from Baseline on the SCoRS at Day 84.
- Change from Baseline on the PANSS total score and additional subscales and factors at Day 84.
- TAK-831 plasma concentrations.

5.1.3 Safety Endpoints

- Percentage of subjects who experience at least 1 TEAE.
- Percentage of subjects who meet the markedly abnormal criteria for safety laboratory tests at least once postdose.
- Percentage of subjects who meet the markedly abnormal criteria for vital sign measurements at least once postdose.
- Percentage of subjects who meet the markedly abnormal criteria for safety electrocardiogram (ECG) parameters at least once postdose.
- Percentage of subjects with treatment-emergent suicidal ideation or suicidal behavior as measured using the C-SSRS.

TAK-831-2002 Statistical Analysis Plan Amendment No. 1

6.0 DETERMINATION OF SAMPLE SIZE

Assuming that the effect size is at least 0.4 for the as 125 mg QD and 500 mg QD doses and that at least 85% of the 234 subjects complete the Day 84 assessment, the study has at least 82% power for at least 1 dose to be statistically significant at the 0.10 level with correction for multiple doses.

7.0 METHODS OF ANALYSIS AND PRESENTATION

7.1 General Principles

Baseline values are defined as the last observed value before the first dose of study medication.

All statistical analyses will be conducted using SAS[®] Version 9.4, or higher, unless otherwise noted.

All confidence intervals, statistical tests, and resulting P-values will be reported as 2-sided and will be assessed at α =0.05 significance level unless otherwise stated. P-values will be rounded to 3 decimal places prior to assessment of statistical significance.

Means and medians will be presented to 1 more decimal place than the recorded data. The standard deviations (SDs) will be presented to 2 more decimal places than the recorded data. Confidence intervals about a parameter estimate will be presented using the same number of decimal places as the parameter estimate.

Where appropriate, variables will be summarized descriptively by study visit. For the categorical variables, the count and proportions of each possible value will be tabulated by treatment group. The denominator for the proportion will be based on the number of subjects who provided non-missing responses to the categorical variable. For continuous variables, the number of subjects with non-missing values, mean, median, SD, minimum, and maximum values will be tabulated.

Screen failure subjects will be grouped and listed at the end.

7.2 Study Definitions

7.2.1 Definition of Study Days

Study Day 1 is defined as the date on which a subject is administered their first dose of doubleblind medication. Other study days are defined relative to the Study Day 1 with Day 1 being Study Day 1 and Day -1 being the day prior to Study Day 1.

7.2.2 Definition of Study Visit Windows

A windowing convention will be used to determine the analysis value for a given study visit that applies to observed data. For each visit, a window will be defined such that the lower and upper bounds of each window is generally the midpoint between 2 consecutive study visits.

More than 1 result for a parameter may be obtained in a visit window. In such an event, the result with the date closest to the scheduled visit day will be used. In the event of 2 observations equidistant to the scheduled visit day, the later of the observations will be used.

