9.0 STUDY PLAN

9.1 Study Procedures

The following sections describe the study procedures to be performed and data to be collected. For each procedure, subjects are to be assessed by the same investigator or site personnel whenever possible. The Schedule of Study Procedures is located in Appendix A.

9.1.1 Alternative Approaches to Study Procedures and Data Collection Due to COVID-19 or Other Unavoidable Circumstances

In unavoidable circumstances (eg, a widespread disease outbreak or natural disaster) that impact the study site's ability to conduct study procedures according to the Schedule of Procedures (Appendix A), contingency measures may be implemented. In acknowledgement of study site, hospital, local, state and national restrictions established in response to circumstances like COVID-19, the following measures are being taken for the current study:

- For subjects impacted while in the double-blind period, all attempts should be made to
 perform the assessments with the subject present at the site using the visit windows.
 Exceptions may be granted for alternative approaches to study procedures and data
 collection through approval by the sponsor or designee. Such instances must be
 documented in the study records and may include the following:
 - Sites must contact the sponsor or designee to discuss individual subject and site circumstances to obtain approval for use of alternative approaches to study procedures and data collection due to COVID-19 or other unavoidable circumstances.
 - Sites may seek approval from the sponsor or designee to continue subjects in the study despite departures from the Schedule of Procedures. The principal investigator is expected to evaluate the impact to the safety of the study participants and site personnel for subjects to continue. In evaluating such requests, the sponsor or designee will give the highest priority to the safety and welfare of the subjects. Subjects must be willing and able to continue taking study medication and remain compliant with the protocol.
 - Other than the final visit, alternative methods for conducting subject visits (eg, video conferencing, telephone visits, or in-home study visits conducted by study site personnel or designated clinical personnel, contingent upon local regulations) may be used per approval by the sponsor or designee:
 - Under these circumstances, collection of certain study assessments may be omitted and visit windows may be extended.

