 - When approval is given for a subject to miss an in-person study visit, a study site physician will speak directly with the subject by telephone or other medium (e.g. a computer-based video communication) during each visit window to assess subject safety and overall clinical status.
 - The study site physician or other qualified site personnel should conduct the following assessments within specified-visit window timeframes: AE assessments, documentation of concomitant medication, administration of C-SSRS, and an assessment of clinical symptoms.
 - Other study assessments may be collected using an alternative method as feasible, and may involve audio or video recording where allowed by local regulation. In some cases, audio and/or video recording of subject interviews may not be

possible and thus will deviate from the planned rater monitoring plan. This will be documented in the study records.

- In some instances sites may need to split visits or sites may only be able to perform a few procedures on site and some procedures may need to be performed remotely. Sites should inform sponsor or designee when this occurs.
- Sites may seek approval to extend a visit window in order to conduct an on-site visit. Assessments that cannot be completed during the protocol-specified window or within the visit window granted by the sponsor or designee will be considered missing data and such departures will be recorded in the study records.
- There will be no interval longer than 8 weeks between visits at which clinical laboratory tests are performed and vital signs are measured. Should this 8 week interval be reached for a particular subject, the site should reach out to the sponsor or designee to discuss withdrawal of the subject.
- Study site personnel may dispense additional investigational medicinal product to subjects at a visit to allow for potentially longer intervals between visits than originally planned per protocol, or investigational medicinal product may be supplied to subjects via delivery by site personnel or by courier.

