- b Randomization is performed at Day 1 (Visit 3). If courier-related delays of laboratory test results occur (eg, due to COVID-19 related factors), Visit 3 may be delayed up to a maximum of 7 days after discussion with and approval from the sponsor or designee. For the screening and Day 1 visits, the study assessments may be conducted over 2 days that must be completed within a 5-day period or less. All Day 1 procedures must be completed and compared with the relevant study entry criteria prior to randomization. The first dose of study drug will be administered in the clinic at the end of the Day 1 visit (or as the last procedure if the Day 1 visit is split over 2 days). Subjects will then take study drug QD in the morning from Day 2 onward during the double-blind treatment period. Study procedures for the Day 84/ET (Visit 10) may be conducted over 2 consecutive days for subject's comfort and assessment feasibility. The final visit (Day 84/ET) should be performed in person. Alternative methods for administering study assessments may be considered when it is not possible for the subject to come to the study site or for the site staff or designated clinical personnel to go to the subject's residence for the final visit (Day 84/ET) in cases where unavoidable circumstance such as the COVID-19 pandemic are prohibitive. Investigators should contact the sponsor or designee to discuss individual subject circumstances (Section 9.1.1).
- For subjects who prematurely discontinue the study, the PANSS, BNSS, BACS, SCoRS, CGI-SCH-I, CGI-SCH-S, and assessments should be performed only in subjects who received at least 1 dose of study drug and are assessed within 1 week of the last dose of study drug; all other ET procedures should be performed for subjects who are assessed >1 week after the last dose of study drug.
- ^d If the date of a subject visit does not conform to the study plan, the timing of the subsequent visits should be planned to maintain the visit schedule relative to randomization.
- ^e In cases where antipsychotic serum levels are not available within the expected 7 days window, additional screening window may be granted in these cases with sponsor or designee approval.
- ^f May be obtained at screening (Visit 1) or placebo run-in (Visit 2) or at the informant's location. The initial discussion with the informant may include an oral informed consent.

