At Baseline (predose Day 1; Visit 3), subjects who continue to meet all eligibility criteria, including placebo run-in drug compliance requirements, will be randomized via an interactive response technology (IRT) system to 1 of the following treatments: TAK-831 50 mg QD, TAK-831 125 mg QD, TAK-831 500 mg QD, and placebo QD. Randomization will be followed by a 12-week Double-Blind Treatment Period (Days 1 to 84), during which subjects will undergo assessments as outlined in Protocol Appendix A. Efforts will be made to perform cognition testing at approximately the same time of day throughout the Double-Blind Treatment Period (postbaseline assessments must be administered ±2 hours from the time of Baseline assessment

administration). A Safety Follow-up Visit (between Days 94 and 98; Visit 11) will be scheduled for all subjects 10 to 14 days after the last dose of study drug.

Subjects will be instructed to take 5 tablets QD during the Single-Blind Placebo Run-in and Double-Blind Treatment Periods, during which time study drug compliance will be monitored with a mobile technology system. Subjects will be instructed to take their study drug with water or milk and to avoid drinking juices 1 hour before and 1 hour after taking study drug.

Subjects who have been screened but have exceeded the 28-day screening period may proceed to the placebo run-in visit after a discussion with the sponsor/designee to obtain approval and to determine whether any screening procedures should be repeated before that study visit.

Subjects who do not meet symptom or medication stability criteria (or other entry criteria that may be met by the subject at a future time) may be considered for rescreening with the approval of the sponsor or designee.

In the event that a subject prematurely discontinues the study, an Early Termination Visit must be conducted, at which time all the assessments scheduled for the Final Visit will be performed.

An interim analysis for futility may be performed during the study, allowing for early study termination if the probability of success on the primary endpoint fails to meet a prespecified criterion. The specifics of this analysis will be included in an interim analysis plan that will be finalized before interim unblinding.

The end of the study is defined as the date the last subject completes the Safety Follow-up Visit (Visit 11).

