7.9 Efficacy Analysis

The analyses and summaries for efficacy will be based on the FAS, unless otherwise noted.

7.9.1 **Primary Efficacy Endpoint(s)**

The primary endpoint is the change from Baseline on the PANSS NSFS at Day 84. The details of PANSS NSFS calculation can be found in Section 7.9.4.

The primary endpoint will be analyzed by comparing TAK-831 and placebo over all assessed time points using estimates from a mixed model for repeated measures (MMRM) with Baseline value as a covariate; pooled site, visit, treatment, and categorical age (randomization factor) as fixed factors; and treatment-by-visit and Baseline-by-visit interactions. Based on a Missing at Random Assumption, this analysis will be performed using observed case data only. The effect at each time point for each treatment is allowed to vary freely and an unstructured covariance matrix is assumed. If the model does not converge, other covariance structures (unstructured, compound symmetry, 2-Toeplitz, etc) will be considered.

Multiplicity will be controlled across dose-arms by first testing the 125 mg QD and 500 mg QD dose-arms in parallel using Holm's method to control the overall type I error rate at the 0.10 level (one-sided), then testing the 50 mg QD dose-arm at the 0.10 level if at least 1 of other doses is found to be statistically superior to placebo.

In order to provide additional insight about dose-response, the primary endpoint may be analyzed using a Multiple Comparison Procedure-Modeling (MCP-Mod) approach (Pinheiro et al, 2014).

For MCP-Mod approach, DoseFinding package in R statistical analysis software will be used. R has been validated by the contract research organization for this study. The following set of models will be fit to detect a dose response: linear, E_{max} , quadratic, and exponential. The stratification factor of age (<35 and \geq 35 years) will be included in the models. Each of the dose-response shapes in these models will be evaluated using optimal contrasts and applying MCP-Mod techniques to preserve the family-wise error rate (FWER) with the overall 1-sided significance level of 0.10. The effective dose(s) will be determined within this framework. The stratification factor of age may be omitted if the dose response for the stratified models cannot be reliably estimated.

The following supplementary analyses will also be conducted for the primary endpoint:

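### Does the SAP need a visit-window table to settle where early-termination PANSS scores go in the primary analysis?

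*SAP*

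**What the plan says.** SAP 7.2.2 defines a window for each visit such that "the lower and upper bounds of each window is generally the midpoint between 2 consecutive study visits". If several results fall in one window, "the result with the date closest to the scheduled visit day will be used", and of two equally distant results the later is taken. The section has no table of day ranges, no rule for a single score lying exactly on a midpoint, and no mention of early termination.

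The schedule in Protocol Appendix A places PANSS, BNSS and CGI-SCH-S after baseline at Days 28, 56 and 84/ET only, out of seven treatment visits. SAP 4.4 says that after premature discontinuation "an Early Termination Visit must be conducted, at which time all the assessments scheduled for the Final Visit will be performed". Appendix A footnote c limits the ratings to subjects who "are assessed within 1 week of the last dose of study drug". Visit 10 carries a joint label in footnote b: "Study procedures for the Day 84/ET (Visit 10) may be conducted over 2 consecutive days".

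For the primary MMRM, SAP 7.9.1 states: "Based on a Missing at Random Assumption, this analysis will be performed using observed case data only". Protocol 9.1.1 allows for unavoidable circumstances in which "collection of certain study assessments may be omitted and visit windows may be extended", and in that setting "Assessments that cannot be completed during the protocol-specified window or within the visit window granted by the sponsor or designee will be considered missing".

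**The concern.** An early-termination PANSS can fall on almost any study day, and the MMRM needs a visit label for it. Take a rating on Day 45. If windows are cut between all visits, it lies in the Day 42 window, where no PANSS is scheduled. If they are cut between PANSS visits only, it becomes a Day 56 value. If the joint Day 84/ET label were taken as an analysis rule, it would be a Day 84 value.

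This bears on the primary endpoint. An observed-case MMRM under missing at random draws on the scores seen up to dropout, and leaving out the last rating before dropout weakens that. Someone who stops on Days 15 to 20 would have no post-baseline value under the all-visit reading, if scores in windows without a scheduled PANSS are dropped. The choice also fixes which visits the placebo-based imputation fills and which CGI-SCH scores count at Day 84 in the Cochran-Mantel-Haenszel test. If it were made after unblinding, it would be open to the charge of being data-driven.

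**Working it through.** **The plan's own figure.** Inputs are arms of 52/52/52/78 (Protocol summary), 85% completion and effect size 0.4 (SAP 6.0), and Holm at one-sided 0.10, hence 0.05 at the first step (SAP 7.9.1).

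- Completers: 78 × 0.85 = 66.3 on placebo and 52 × 0.85 = 44.2 per dose.
- Per dose: 0.4/√(1/66.3 + 1/44.2) − 1.645 = 2.060 − 1.645 = 0.415, so power is 66.1%.
- The two comparisons share placebo, with correlation 44.2/(44.2 + 66.3) = 0.40. Power for at least one dose is 82.8%, which agrees with the stated 82%. Windows do not enter this calculation.

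**Windows under the two date-based readings**, with midpoint days given to the later visit and follow-up taken as Day 96:

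| Reading | Day 28 | Day 56 | Day 84 |
|---|---|---|---|
| All visits (midpoints 21, 35, 49, 63, 77, 90) | 21–34 | 49–62 | 77–89 |
| PANSS visits only (midpoints 14.5, 42, 70) | 15–41 | 42–69 | 70 onward |

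**Scheduled visits.** Appendix A allows ±2 days at Days 28 and 56 and ±5 at Day 84, that is 26–30, 54–58 and 79–89. All lie inside the matching window under both readings, so every on-time rating gets the same label.

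**Early-termination scores.** The documents give no timing. Assume termination uniform over Days 2–83 (82 days) and earlier visits attended on schedule. By the closest-date rule, an early-termination score is then used only if no attended visit lies in its window.

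- All visits: Days 21–28 (8) + 49–56 (8) + 77–83 (7) = 23 of 82 (28%).
- PANSS visits only: Days 15–28 (14) + 42–56 (15) + 70–83 (14) = 43 of 82 (52%).
- Difference: Days 15–20 (6) + 42–48 (7) + 70–76 (7) = 20 days. With midpoint days given to the earlier visit the counts are 20 and 41, a difference of 21.

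**In subjects.** Non-completers number at most 234 × 0.15 = 35.1, because the plan assumes at least 85% complete.

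- All rated: 35 × 20/82 = 8.5, or 35 × 21/82 = 9.0.
- Half rated: 4.3 to 4.5.
- Gaining a Day 84 value: 35 × 7/82 = 3.0.
- With no other post-baseline value (Days 15–20): 35 × 6/82 = 2.6.

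Under other assumed timings (linear early or late; exponential with half-life 14, 28 or 42 days) and all rated, the difference is 6.6 to 9.4 of 35. It reaches 9.7 with midpoint days given to the earlier visit. These ranges reflect the distributions chosen and are not bounds from the documents.

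**The label reading.** SAP 7.2.2 assigns by date, with bounded windows and a closest-date rule. Counting a Day 10 score as Day 84 contradicts that. Day 84/ET is a column in a procedure schedule, so only the first two readings are in play.

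**The case for a change.** The best case for amending the SAP is that this is the primary endpoint, the rule has two workable readings, and a short table fixed before unblinding would cost almost nothing. Neither reading is compelled. The word *generally* is open-ended, and the tie rule covers two results in one window, not one result on a boundary. That much stands: the text does not settle the matter, and a line in the programming specification is worth having.

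The rest is weaker. That scores in the Day 7, 14, 42 or 70 windows would be dropped is an inference; the SAP does not say whether they are dropped, moved to a PANSS visit or added as a visit level. The Protocol 9.1.1 sentence on missing assessments concerns extended windows in unavoidable circumstances and is not a general missing-data rule.

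Nor is there one right table. Cutting between PANSS visits brings in more scores but places some of them up to 14 days from the scheduled day (Day 70 counted as Day 84). For BACS, scheduled at Days 42 and 84, the distance reaches 21 days (Day 63 counted as Day 84). Cutting between all visits keeps scores within about 7 days and uses fewer. Scores on Days 2–14 are nearest to baseline under the PANSS-visit reading. For SCoRS, rated only at Days 1 and 84, a strict midpoint would admit scores from Day 43. Competent statisticians could choose differently on each of these.

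**Conclusion.** No change to the plan follows. This is missing detail of the kind analysts fill sensibly. Windows based on the visits that schedule the assessment are a routine specification, and the SAP's wording already permits them. Protocol 13.1 provides for a blinded data review before unblinding, covering subject evaluability and the planned methods, and that is a natural point at which to fix the day ranges.

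The choice affects only non-completers. It concerns about 9 of at most about 35 if all have a rating and about 4 if half do, spread over four arms; about 3 would gain a Day 84 value. These figures assume uniform termination over Days 2–83 and scheduled attendance until then. On-time visits and the 82% power are unchanged. The direction and size of any bias cannot be derived from the documents, and no wrong result has been shown.

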7.2.3 Conventions for Missing Adverse Event Dates

Incomplete adverse event (AE) start dates will be imputed to determine the relationship between the start date and the informed consent date, as well as the start date and the first dose date of the double-blind study medication. Incomplete AE dates will be presented as they are in the listings.

TAK-831-2002	Page 15 of 30
Statistical Analysis Plan Amendment No. 1	01 February 2021

The following methods will be used to impute incomplete start dates of AEs:

- If only the month and year of the start date are available and the month and year are different than the month and year of the first dose of double-blind study medication or the stop date is prior to the first dose of study medication, then the first day of the month will be used for the start date. If only the month and year of the start date are available and the month and year are the same as the month and year of the first dose of double-blind study medication and the stop date is not prior to the date of first dose, then the date of first dose will be used for the start date.
- If only the year of the start date is available and the year is different than the year of the first dose of double-blind study medication or the stop date is prior to the first dose of study medication, then January 1st will be used for start date. If only the year of the start date is available and the year is the same as the year of the first dose of double-blind study medication and the stop date is not prior to the date of first dose, then the date of first dose will be used for start date.

